Artificial intelligence for mental health diagnoses and treatment plans: A protocol for actors and patients.

[name]

[name]

[name]

Ver. 2.3

27.03.2024

Background

Artificial intelligence (AI) is becoming prevalent in modern medicine and psychiatry. AI is based upon a wide variety of computer algorithms classified under machine learning (ML). Beginning in the 1960s, a computer program known as ELIZA was developed to emulate psychotherapists' conversational abilities. By simulating human conversation, the machine would help the patient do most of the cognitive work of interpretation. As a result of the program, the field of artificial intelligence has expanded rapidly, initially intended only for research purposes involving natural language processing experiments. In 1971, another computer model was designed to simulate paranoia in a diagnostic psychiatric interview. An attempt was made to characterize the inner structure of paranoid behavior often encountered by clinicians when interviewing paranoid patients (Pham et al, 2022).

Artificial intelligence algorithms were able to identify healthy patients from patients with psychotic disorders with an accuracy of more than 70%. Artificial intelligence has been used in studies to examine speech disorders and differentiate speech samples from patients with psychotic disorders from healthy controls. Algorithms could detect where speech sample incoherence occurred, predict levels of incoherence, and were sensitive to very subtle deviations in long clinical interviews (Ray et al, 2022).

The purpose of the present study is to evaluate this potential, using AI. It will conduct an interview with standardized SP patients (actors) presenting a psychiatric illness, and based on the interview, it will present a differential diagnosis and treatment plan. Immediately afterwards, the actors will be interviewed by a board certified psychiatrist, who will also give a differential diagnosis and a treatment plan. The results of the AI and psychiatrist will be compared. In the second part of the study, AI will examine patients coming for consultation by a psychiatrist in the inpatient units, outpatient units or in the emergency room (ER) in Sheba. The patient will give informed consent, and will be interviewed by AI. The interview will be done either digitally, or will use to voice-to-text and text-to-voice technology that will allow the patient to speak with the computer, instead of typing questions into the computer. Future studies, not included in the current proposal, will use voice analysis, face recognition and computerized emotion recognition as part of AI.

Methods

Participants:

1. Five actors SPs, each time employed by MesserMSR, the Israeli Center for Medical Simulation, trained to simulate symptoms of psychiatric illnesses.
2. Patients (n=200) treated in the Division of Psychiatry in the Sheba Medical Center. In addition, patients who applied for treatment in the psychiatric clinic in the Division of Psychiatry in the Sheba Medical Center but are not yet treated there, and patients treated in the psychiatric emergency room (ER) in Sheba. In addition, a recruitment ad will be published in the media and on social networks, to include patients who will come in specifically to participate in the study.
3. Ten board certified Psychiatrists from the Drora and Pinchas Zachai Division of Psychiatry in the Sheba Medical Center.

Scenarios for actors:

The actors will be trained in one of 5 scenarios: depression, anxiety, PTSD with cannabis abuse, psychosis and control patient with no diagnosis. Each scenario will have 2 levels of severity. The actors will present demographic and medical background, symptoms and signs, including disorders of thought and affect.

Procedure:

Actors or patients will be interviewed by AI. The interview will either be digital or will utilize AI voice to text and text to voice technology, so that the participant will be speaking with the application which will respond vocally. After the AI interview the participant will be interviewed by a board-certified psychiatrist, who will determine the differential diagnosis and recommend treatment. Both, the AI and the psychiatrist, interviews will be audiotaped. The entire procedure will be repeated twice, for two days. After that, technological improvements will be made in AI. For the third time, the SPs will play against the AI only to check that the technological changes made didn't harm the quality of the AI.

Proposed schedule for actors

Time line		AI session 1

	1	Depression Low severity	Anxiety Low severity	PTSD with cannabis abuse Low severity	Psychosis Low severity	Control patient
	2	Depression High severity	Anxiety High severity	PTSD with cannabis abuse High severity	Psychosis High severity	Control patient
		Face to face phase *				
		Doctor 1		Doctor 2	Doctor 3	Doctor 4
	3	Depression Low severity	Anxiety High severity	PTSD with cannabis abuse Low severity	Psychosis Low severity	Control patient
	4	Psychosis High severity	Depression Low severity	Anxiety Low severity	PTSD with cannabis abuse Low severity	Control patient
	5	PTSD with cannabis abuse High severity	Psychosis Low severity	Depression High severity	Anxiety High severity	Control patient
	6	Anxiety Low severity	PTSD with cannabis abuse High severity	Psychosis High severity	Depression High severity	Control patient
		AI session 2 **				
	7	Depression High severity	Anxiety High severity	PTSD with cannabis abuse High severity	Psychosis High severity	Control patient
	8	Depression Low severity	Anxiety Low severity	PTSD with cannabis abuse Low severity	Psychosis Low severity	Control patient

* We can choose any other balance of disorder and severity between doctors.

** two AI sessions to overcome the question per hour limit.

*** We will set the exact schedule prior to the training. The study should take half a day. 3:30-4 hour day.

For the actor's part of the project, over all there will be 125 encounters, 75 with AI and 50 with a psychiatrist in 3 days. The interviews of the actors and psychiatrist in MSR will be videotaped, so that in the future voice and facial analysis can be integrated into the project.

For the patient's part of the project, 200 patients will be interviewed by AI and then by a psychiatrist. This includes patients treated in the Division of Psychiatry in the Sheba Medical Center. In addition, patients who applied for treatment in the psychiatric clinic in the Division of Psychiatry in the Sheba Medical Center but are not yet treated there, and patients treated in the psychiatric emergency room (ER) in Sheba. In addition, a recruitment ad will be published in the media and on social networks, to include patients who will come in specifically to participate in the study.

For patients arriving for intake at the clinic - the study coordinator will contact them before the appointment, and ask them to arrive an hour earlier for the study. These patients will be paid NIS 100 for their time and travel reimbursement.

For patients who are on the waiting list, the study coordinator will contact them and explain that they can participate in the study: will be examined by Liv and then receive a psychiatric examination by a psychiatrist. The examination will be performed for research purposes only, the patient will receive a brief letter to the family doctor with the diagnosis and recommendations for treatment .

The first approach to the patient will be made in an SMS, the wording will be (Hebrew below):

"Dear Sir/Madam,

"At the Sheba Medical Center, a study is currently being conducted on the topic: "Artificial intelligence to be used as a diagnostic tool in mental health and recommendations for a treatment plan." And we would like to offer you to participate in it.

If you have no objection, we will contact you by phone in the coming days for a short questionnaire.

Any information provided during the interview will remain confidential and will be used for research purposes only.

Your response to the research will contribute to the understanding of the researched topic and the expansion of general knowledge.

If you are not interested in participating in the study or hearing more details about it, please reply to this message "not interested".

If the patient does not answer because he is not interested. The research coordinator will contact you by phone.

For social media ads, the wording will be (Hebrew below):

"Participants are needed for a research study

In the psychiatric department at Haim Sheba Tel Hashomer Hospital, a groundbreaking study is currently underway on the subject:

"Artificial intelligence to be used as a diagnostic tool in mental health and recommendations for a treatment plan."

As part of this study, we are recruiting men and women over the age of 18. The main purpose of the study is to compare the results of the AI system test with the results of a psychiatrist's examination.

Participation in the study includes arriving at the Sheba Tel Hashomer Hospital for examination by the AI system and a psychiatrist. It will be possible to receive the summary of the meeting with the psychiatrist. Expenses will be reimbursed in the amount of NIS 100.

The details of the subjects will be kept confidential

Those interested in participating are welcome to send a text/WhatsApp message

[contact]

In addition, all participants in the study will be asked to fill out a satisfaction questionnaire (attached Appendix 1). And the examining psychiatrists will be asked to fill out a form of diagnosis, severity and recommendations for drug and psychotherapeutic treatment (attached in Appendix 2). This interview will be audiotape.

The primary outcome of the study will be a comparison of the interviews, differential diagnoses and recommendations for treatment assigned by the AI with those assigned by the board certified psychiatrist. the rates of agreement will be the outcome of interest.

All actors, patients, and psychiatrists participating (The psychiatrists who participate in the actors part) will give informed consent.

security and privacy:

1-Actors in MSR: The interviews will be recorded and stored in the Simboost server managed by MSR.

2-Patients in the Division of Psychiatry and ER: after giving informed consent, the investigators will enter the patients ID number into a conversion table, so that each patient will receive a code number which will identify the patient for AI.

The conversion table and the audiotape interviews will be stored in the Sheba secured server, which be accessed only by the research team.

Statistical Analysis Plan

Data

Actors who simulate one of four psychiatric illnesses (anxiety, depression, PTSD, or Mania) or a control condition that is not considered psychotic) are interviewed by a psychiatrist or a computerized AI program (called Liv), and for each interview the following is recorded:

- (i) Interviewer (psychiatrist or Liv)
- (ii) If psychiatrist, identity number
- (iii) True diagnosis
- (iv) True severity (mild/severe)
- (v) Medication indicated
- (vi) Psychiatric treatment indicated
- (vii) Primary diagnosis made
- (viii) Secondary and Tertiary diagnoses made
- (ix) Severity (mild/moderate/severe)
- (x) Medications recommended
- (xi) Psychiatric treatment recommended

The codes 0, 5 (no diagnosis) and 9 (adjustment disorder) are taken to be equivalent diagnoses in the analyses described below.

Analyses

Note that in the analyses below, all estimated percentages will be accompanied by a 95% confidence interval.

- (a) Diagnosis:

The overall results will be summarized as:

1. % agreement of the primary diagnosis with gold standard over all conditions: (i) for Liv; (ii) for psychiatrists.
2. % agreement between Liv and psychiatrists; this calculation will need a special method – see paragraph (f) below.
3. The results will be displayed also as cross-tabulations of the 5 conditions according to gold standard versus Liv, according to gold standard versus psychiatrists, and according to psychiatrists versus Liv.
4. Analyses 1, 2, and 3 above will be repeated under the rule that agreement with the gold standard is achieved if one of the diagnoses (primary, secondary or tertiary) agrees with the gold standard, and agreement with the psychiatrists is achieved if one of the Liv diagnoses (primary, secondary or tertiary) agrees with the primary diagnosis of the psychiatrist.

(b) Diagnosis according to severity of condition:

The following analyses will be conducted:

5. As in 1 and 2 above, but for severe conditions only.
6. As in 1 and 2 above, but for mild/moderate conditions only.
7. As in 3 above, but for severe conditions only.
8. As in 3 above, but for mild/moderate conditions only.
9. As in 4 above, but for severe conditions only.
10. As in 4 above, but for mild/moderate conditions only.

(c) Diagnosis and Severity:

Note that throughout, **mild and moderate severity assessments will be considered equivalent**. If the psychiatrist or Liv classifies a patient with mild severity as having moderate severity, this will not be counted as an error.

Severity assessments will be evaluated in two different ways:

First, they will be included as part of the definition of a correct classification: e.g. a patient with severe anxiety will be considered correctly classified only if the psychiatrist or Liv classifies them as having severe anxiety. A classification of mild/moderate anxiety will be counted as an error. Analyses using this type of evaluation are listed below.

11. As in 1 and 2 above.

12. As in 3 above, but here the table will be a 9 x 9 cross-classification, with the following categories: mild anxiety, severe anxiety, mild depression, severe depression, mild PTSD, severe PTSD, mild Mania, severe Mania, control.

Second, **within the set of correctly assigned primary diagnoses**, we will do the following analyses:

13. % agreement of assigned severity scores with the gold standard (i) for Liv and (ii) for psychiatrists.

14. % agreement of assigned severity scores by Liv versus that assigned by the psychiatrists.

15. The results will be displayed also as 2 x 2 cross-tabulations of the 2 severities according to gold standard versus Liv, according to gold standard versus psychiatrists, and according to psychiatrists versus Liv.

(d) Medications and psychiatric treatments:

Agreement of the recommendations provided by Liv and by the psychiatrists will be compared with the gold standard. As with the second approach to evaluating severity assessments, the comparisons will be made only **within the set of correctly assigned primary diagnoses**.

There will be only one primary gold standard medication (psychiatric treatment), and the recommendation by Liv or the psychiatrist will be judged correct only if it includes this primary medication (psychiatric treatment).

Thus the two main analyses will be:

16. % agreement with primary gold-standard medication of (i) Liv's recommended medication and (ii) psychiatrists' recommended medication.

17. % agreement with primary gold-standard psychiatric treatment of (i) Liv's recommended treatment and (ii) psychiatrists' recommended treatment.

(e) Decision thresholds:

On the basis of certain of the above statistics, we specify two conditions that must be satisfied for Liv to proceed to the Phase II study that involves real patients arriving for diagnosis and treatment at Sheba Medical Center.

A. The % agreement of the psychiatrists' primary diagnosis with the gold standard is >85%.

If it falls below this value, then it will be concluded that the "simulation" was not sufficiently realistic and some adjustments to the training of the actors will need to be made.

B. The % agreement of Liv's primary diagnosis with the psychiatrists' primary diagnosis >85%. If it falls below this value, then it will be concluded that adjustments are required to the Liv program.

Reference

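### Liv is changed before the third actor day, but the SAP records no day or Liv version and plans no analysis that separates that day

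*Combined protocol and SAP*

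**What the plan says.** The Procedure section describes AI and psychiatrist interviews of the actors on two days. It continues: "After that, technological improvements will be made in AI". The third occasion has no psychiatrist: "For the third time, the SPs will play against the AI only to check that the technological changes made" have not made the AI worse. The text under the actor schedule gives the volume: "over all there will be 125 encounters, 75 with AI and 50 with a psychiatrist in 3 days". The 75 Liv encounters therefore include the third day.

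The SAP's Data section says that actors "are interviewed by a psychiatrist or a computerized AI program (called Liv), and for each interview the following is recorded", followed by items (i) to (xi). These cover the interviewer, an identity number if the interviewer is a psychiatrist, the true condition and severity, the indicated treatments, and the diagnoses, severity and treatments assigned. Day, date, session and Liv version are not among them.

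Analysis 1 is the percentage "agreement of the primary diagnosis with gold standard over all conditions: (i) for Liv; (ii) for psychiatrists". Analysis 2 is the percentage "agreement between Liv and psychiatrists; this calculation will need a special method", with the method referred to a paragraph (f). In the supplied text the lettered sections end at (e). Section (e), Decision thresholds, sets "two conditions that must be satisfied for Liv to proceed to the Phase II study that involves real patients". Gate B, one of the two, requires more than 85% agreement between Liv's and the psychiatrists' primary diagnoses. It names neither a day nor a Liv version.

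**The concern.** The Procedure section gives the third day one purpose: to show whether the changed Liv is worse than the Liv of days 1-2. Answering that needs a before-and-after contrast, and the SAP has neither the fields nor an analysis for it. If every Liv interview enters analysis 1(i), a loss or gain from the change is diluted into one percentage that describes no single version of the program. The same applies to the other comparisons of Liv with the gold standard. If day 3 is left out instead, its data have no planned use.

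There is also a consequence for the step to patients. Gate B compares Liv with psychiatrists, and day 3 has no psychiatrist interviews, so the natural reading is that B uses days 1-2. On that reading B describes Liv before the change, and the documents do not say whether that version or the changed one will interview patients.

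**Working it through.** **1. Inputs from the documents.** There are 75 Liv and 50 psychiatrist encounters over 3 days. Liv takes part on all three days and psychiatrists on two. The printed schedule has four Liv rows per day (1, 2, 7, 8) and four face-to-face rows (3 to 6), with five actors.

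**2. Encounter count.**
- Stated totals: 75/3 = 25 Liv interviews per day and 50/2 = 25 psychiatrist interviews per day; 75 + 50 = 125.
- Printed schedule: 4 x 5 = 20 of each per day, so 3 x 20 = 60 Liv and 2 x 20 = 40 psychiatrist interviews, 100 in all.

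The schedule does not reproduce 125, but it is labelled as proposed, with details to be set later. Both counts are carried below. With equal numbers per day, day 3 supplies 25/75 = 20/60 = one third of the Liv data either way.

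**3. Fields and analyses.** Items (i) to (xi) identify the psychiatrist but not the Liv version or the day. Analyses 1 to 17 divide the data by condition, severity, rank of diagnosis and treatment, never by day or version. The documents give no margin or criterion for harm.

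**4. What a single Liv percentage would report.** Let p1 be accuracy against the gold standard on days 1-2 and p2 on day 3. The expected pooled figure is (2 x p1 + p2)/3. All rates here are assumed; the documents give none.

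| p1 | p2 | Pooled |
|---|---|---|
| 92% | 72% | (1.84 + 0.72)/3 = 85.3% |
| 92% | 82% | (1.84 + 0.82)/3 = 88.7% |
| 92% | 87% | (1.84 + 0.87)/3 = 90.3% |
| 80% | 92% | (1.60 + 0.92)/3 = 84.0% |

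Pooling can hide a gain as well as a loss. In counts, the first row could be 46/50 (exact 95% interval 80.8% to 97.8%) and 18/25 (50.6% to 87.9%). The single figure would then be 64/75 = 85.3% (75.3% to 92.4%).

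**5. What a separate analysis could show.** For a difference d = p2 - p1, Newcombe's interval combines the Wilson limits (l1, u1) for days 1-2 and (l2, u2) for day 3:
- lower = d - sqrt[(p2 - l2)^2 + (u1 - p1)^2]
- upper = d + sqrt[(u2 - p2)^2 + (p1 - l1)^2]

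*Equal results, 22/25 and 44/50 (both 88%).* The Wilson limits are 0.7004 to 0.9583 and 0.7620 to 0.9438.
- lower = -sqrt(0.1796^2 + 0.0638^2) = -0.191
- upper = sqrt(0.0783^2 + 0.1180^2) = 0.142

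The interval is about -19 to +14 points. On its own, 22/25 has an exact interval of 69% to 97%.

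*The counts in step 4, 18/25 and 46/50.* The Wilson limits are 0.5242 to 0.8572 and 0.8116 to 0.9685.
- lower = -0.20 - sqrt(0.1958^2 + 0.0485^2) = -0.402
- upper = -0.20 + sqrt(0.1372^2 + 0.1084^2) = -0.025

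Separate reporting would show this fall; the pooled figure would not.

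*How often the interval lies wholly below zero,* summing binomial probabilities over all outcomes, with 92% on days 1-2:

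| True day-3 rate | 25 v 50 | 20 v 40 |
|---|---|---|
| 72% | 62% | 51% |
| 82% | 25% | 20% |
| 87% | 10% | 8% |

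All of step 5 treats interviews as independent. Repeated interviews of a few actors would probably carry less information.

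**The case against.** **No SAP sentence says that day 3 enters analyses 1 to 17.** This is correct. A reader might infer that the SAP has decided to pool the two versions, but the documents do not support that. Pooling is only the default reading of one Liv percentage with no exclusion. The gap remains either way: including day 3 mixes versions, and excluding it leaves the harm check without an analysis.

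**Paragraph (f) may settle gate B.** It may, and it is not in the supplied text. A reader might go on to calculate how often B would pass under different uses of day 3. That is not supportable, because it would assume one agree-or-disagree result per Liv interview while the actual method is unknown. Nor can days 1-2 be treated as one-to-one pairs. The purpose statement says "Immediately afterwards, the actors will be interviewed by a board certified psychiatrist", but schedule rows 7 and 8 put Liv interviews after the face-to-face phase. No error in the gate decision has been shown. The missing fields and the gold-standard analyses do not depend on (f).

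**The day could be recovered from recordings.** Probably so, which means the harm question is unplanned rather than unanswerable. A split made after the results are known is weaker than one written beforehand.

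**Day 3 is too small to settle the matter.** This stands as a limit on what the analysis can show, as step 5 makes plain. It is a reason to report an estimate with its interval, not to merge the versions.

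**The Procedure and Decision thresholds sections might seem to conflict,** since one plans changes to Liv and the other calls for adjustments if B fails. They do not conflict; both can happen.

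**Conclusion.** The point holds as a gap in the plan that should be fixed before analysis. The protocol changes Liv after day 2 and gives day 3 a purpose, but the SAP records nothing that would identify the version and plans no analysis that serves that purpose. On the default reading, the changed version contributes one third of every overall Liv percentage against the gold standard. A 20-point fall from 92% would then appear as about 85%, a 10-point fall as about 89%, and a 5-point fall as about 90%. These sizes rest on assumed accuracies and equal numbers of Liv interviews per day. The absence of the fields and of the comparison rests on the text alone.

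For gate B the conclusion is narrower: the version is not named in the supplied text. If days 1-2 are meant, B describes Liv before the change, which may not be the version that patients meet.

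**What to change.** 1. Add interview day and Liv version to the recorded fields.
2. Report Liv's agreement with the gold standard, at least analysis 1(i), separately for days 1-2 and day 3.
3. Prespecify the harm analysis as the day 3 minus days 1-2 difference in primary-diagnosis accuracy against the gold standard, on the same scenario and severity mix, with a 95% interval. If day 3 repeats the same grid this is the simple difference; otherwise weight to a common mix.
4. State in one sentence which Liv version and which interviews gate B uses, without pooling versions, and which version goes to patients.

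The cost is two data fields and a few lines of SAP text, with no added interviews. The drawback is precision. With about 20 to 25 interviews on day 3, even identical observed results leave an interval of roughly -19 to +14 points (22/25 against 44/50), so only large harm can be revealed. The result should be presented as an estimate, and a wide interval that includes zero should not be read as proof of no harm.

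### Scoring adjustment disorder as no diagnosis raises condition A, and possibly condition B, and the SAP plans no result with the codes kept apart

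*Combined protocol and SAP*

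**What the plan says.** The protocol (Methods, Scenarios for actors) lists five scenarios: "depression, anxiety, PTSD with cannabis abuse, psychosis and control patient with no diagnosis". The Data part of the SAP describes the fifth more loosely, as "or a control condition that is not considered psychotic".

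The coding rule closes the Data part: "The codes 0, 5 (no diagnosis) and 9 (adjustment disorder) are taken to be equivalent diagnoses in the analyses described below". It gives no reason and makes no exception.

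The analyses that follow include:

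- Item 1: "agreement of the primary diagnosis with gold standard over all conditions: (i) for Liv; (ii) for psychiatrists".
- Item 2: "agreement between Liv and psychiatrists; this calculation will need a special method – see paragraph (f) below".
- Item 3: cross-tabulations of the five conditions.
- Item 4: a repeat of items 1–3 under a looser rule, in which "agreement with the gold standard is achieved if one of the diagnoses (primary, secondary or tertiary) agrees with the gold standard".

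Section (e), Decision thresholds, takes two of these statistics as "conditions that must be satisfied for Liv to proceed to the Phase II study". Condition A is the psychiatrists' primary-diagnosis agreement with the gold standard. Condition B is Liv's primary-diagnosis agreement with the psychiatrists. Each must exceed 85%.

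**The concern.** Adjustment disorder is a psychiatric diagnosis, and the control is defined by having none. Under the merged coding, a psychiatrist who gives a control adjustment disorder is credited with a correct answer in condition A. Liv receives the same credit in item 1. In condition B, an interview pair in which one rater gives code 9 and the other gives 0 or 5 is credited as agreement.

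The planned output would not show how often this happens. The five-condition tables in item 3 and the 9 × 9 table in item 12 each have one control category, and no run with code 9 kept separate is planned. The people deciding whether Liv goes on to real patients would see a percentage above 85% without knowing how much of it rests on the merging.

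Item 4 has a separate weakness. A control given depression first and adjustment disorder second or third is scored as correctly classified, because one of the three listed diagnoses matches the merged no-diagnosis category.

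**Working it through.** **Encounter numbers.** The protocol states 125 actor encounters, 75 with AI and 50 with a psychiatrist, and 75 + 50 = 125. The printed schedule does not reproduce this. It has four AI rows and four face-to-face rows of five, so 20 of each per day. Three AI days and two psychiatrist days give 60 + 40 = 100. A day of 25 of each would give 75 and 50. The two should be reconciled, but the control share does not depend on it.

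**Control share.** Every printed row has one control in five cells, so the share is 20%. If all rows follow this pattern, 50 psychiatrist interviews include 10 controls and 75 Liv interviews include 15. On the printed grid, 40 psychiatrist interviews include 8.

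**Credit in condition A.** Let q be the share of controls to whom the psychiatrists give code 9 as primary diagnosis. Credit = 20 × q percentage points. The documents do not give q, so it is shown as a range:

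| q | Credit (points) |
|---|---|
| 10% | 2 |
| 30% | 6 |
| 50% | 10 |
| 100% | 20 |

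With 10 controls among 50 interviews, q = 10% is one interview, or 1/50 = 2 points. The same formula applies to Liv's agreement with the gold standard in item 1, using Liv's own q.

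**Extreme case.** With n = 50, 0.85 × 50 = 42.5, so 43 agreements (86%) are needed. If all 10 controls are labelled code 9, the condition is met with 33 of 40 illness scenarios correct (82.5%), and strict agreement is 33/50 = 66%. With n = 40, 0.85 × 40 = 34, so 35 are needed. Then 27 of 32 (84.4%) suffices, and strict agreement is 27/40 = 67.5%.

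**Chance of meeting condition A, n = 50 (illustrative).** Let a be the accuracy in illness scenarios, and suppose every control is given 0/5 or 9. Merged: P(X + 10 ≥ 43), with X binomial(40, a). Strict: P(X + Y ≥ 43), with Y binomial(10, 1 − q). Interviews are taken as independent.

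| a | Merged | Strict, q = 10% | Strict, q = 30% |
|---|---|---|---|
| 80% | 0.44 | 0.30 | 0.11 |
| 85% | 0.76 | 0.60 | 0.30 |
| 90% | 0.96 | 0.88 | 0.60 |
| 95% | 1.00 | 0.99 | 0.89 |

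At a = 90% and q = 30%, expected agreement is 0.8 × 90 + 20 = 92% merged and 0.8 × 90 + 20 × 0.7 = 86% strict. Both a and q are assumed.

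**Condition B.** Merging adds credit only for pairs in which one rater gives 9 and the other gives 0 or 5. Such pairs can also arise for an actor playing an illness. If both raters label every control code 9, they agree under strict scoring too and the credit is zero, so 20 × q does not apply. The method for Liv–psychiatrist agreement is deferred to a paragraph (f) that is not in the text available, so no figure can be given.

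**The case against.** The rule is explicit and pre-specified, so it is a lenient choice and not a contradiction. The individual diagnoses are recorded, so the split could be tabulated later. The SAP's looser description of the control might hint that mild distress was expected. Condition A checks whether the actors' simulation was realistic; it does not test Liv. With q near 10%, the effect at n = 50 is about one interview. All of this stands and limits the size of the point. It does not supply a rationale, and a table that could be made later is not a planned one.

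A reader might infer more than the documents support:

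- *Any psychiatric diagnosis in a control counts as correct.* Only adjustment disorder is excused. Depression, anxiety or any other primary diagnosis in a control remains an error against the gold standard.
- *The 20 × q credit applies to both conditions.* It applies to agreement with the gold standard, so to condition A and item 1. Neither condition compares Liv with the gold standard.
- *Item 4 helps Liv to proceed.* Both conditions use the primary diagnosis only, so the any-of-three rule cannot move the decision.
- *Every control is scored correct in item 4 because empty lines are coded 0.* The documents do not say how an empty line is coded, and a control given three disorders would have none.
- *Over-diagnosis is hidden altogether.* The five-condition tables still show controls given another listed disorder, and false positives for each disorder among actors playing a different one. Only the split between code 9 and codes 0/5 is lost.

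**Conclusion.** The point holds as a lenient scoring choice that the SAP neither justifies nor tests. For condition A, and for Liv's gold-standard agreement in item 1, the credit is 20 × q points. This rests on a 20% control share, which the schedule supports, and on a q that the documents do not give. At 10% the effect is small. At 30% it can plausibly decide whether condition A is met, under the accuracies and independence assumed above. The fall from 86% to 66% is the limit when every control is labelled code 9, not a forecast. For condition B only the direction is known: merging cannot lower simple pairwise agreement, but the amount cannot be computed. The weakness in item 4 is real but does not touch the decision to proceed.

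**What to change.** Keep the merged coding as planned, give the reason for it, and make three changes to the SAP:

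1. Report conditions A and B and analyses 1–3 a second time, with code 9 as its own category.
2. State in section (e) that a condition met only under the merged coding will be flagged as such in the decision to proceed.
3. In analysis 4, score control encounters on the primary diagnosis only, as in analysis 1. A second or third code 9, or an empty line, then cannot turn a primary disorder into agreement. Controls are treated no more strictly than in analysis 1, and the relaxation remains for the illness scenarios.

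The cost is a few lines of SAP text and one repeat of existing tables, with no new data. The drawback for the sponsor is that the second percentage may be less favourable.
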